Study Population: Recipient subjects will be hospitalized patients aged 18 years or older with severe or life-threatening COVID-19 disease within 21 days or less from beginning of illness. Donor subjects will be people aged 18 years or older who are able to donate blood per standard blood bank guidelines; have prior diagnosis of COVID-19 documented by a laboratory test; and have complete resolution of symptoms at least 28 days prior to donation.

Study Duration: April 1, 2020 to December 31, 2022

Study Design: This a prospective open label pilot study to assess the feasibility of delivering anti-SARS-CoV-2 convalescent plasma to hospitalized patients aged 18 years of age or older, with severe or life-threatening COVID-19 disease less than 21 days from the beginning of their illness. We plan a targeted recruitment of 100 total eligible donor to donate plasma. A total of 10 eligible recipient subjects will receive anti-SARS-CoV-2 plasma after eIND application to the FDA has been approved for each individual subject.

The following will be assessed in all donor subjects

- Biomarker tests performed in the research lab (e.g. antibody titer, cytokine levels)
- Donor questionnaire
- Donors screened as above must be otherwise eligible, give consent, and successfully donate plasma, as part of a whole blood (WB)

The following will be assessed in all recipient subjects:

- Feasibility: is plasma given to the recipient
- All demographic and clinical data contained in the electronic medical record, as well as hospital administrative data for enrolled patients. This data includes age, sex, comorbidities, date of symptom onset, type of admission, APACHE score, SOFA score, clinical status, vital signs including temperature, respiratory rate, oxygen saturation, oxygen requirement, CBC with neutrophil counts, lymphocyte count, complete metabolic panel, liver function tests, CRP, chest x-ray, chest CT, location in hospital.
- Safety and efficacy: Day 0 (baseline), 1, 2, 3, 7, 14, and 28 and once monthly at 2-3 months.

- SARS-CoV-2 PCR from nasopharyngeal swabs: Day 0, 3, 7, 14 to assess viremia response. Other clinically-approved SARS-CoV-2 testing may be used if available (e.g. saliva, nares, blood).
- Biomarker tests performed in the research lab (e.g. antibody titer, cytokine levels) on day 0, 1, 3, 7, 14, additional days 21 and 28 may be included, as available.

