Evaluate the safety of investigational treatment with anti-SARS-CoV-2 plasma in hospitalized patients with severe or life-threatening COVID-19

Secondary Objectives:

Biomarker tests performed in the research lab (e.g. antibody titer, cytokine levels) at days 0, 1, 3, 7 and 14 (additional days 21 and 28 may be included, as available) in the recipient.

Measure rates, levels and duration of SARS-CoV-2 RNA in nasopharyngeal swabs using RT-PCR among recipients. Other specimen types may be tested as available (eg., BAL fluid, tracheal secretions, sputum, etc.) or when RT-PCR assays are validated for additional sources (i.e., stool, blood).

Definitions

- Enrolled: From time consented to participate until designated as a screen failure or have either been discontinued from the study or completed it.
- Screen Failures: signed informed consent, but then determined to be ineligible or withdraws
- Discontinued: withdrawn by investigator or withdraws consent
- Completed: Subjects are considered to have completed when they are followed through day 90 or have had an adverse event or death occurred prior to day 90.

Study population

Plasma Donor Subject Inclusion Criteria for Enrollment

- Age 18 or older
- Able to donate blood per blood bank standard guidelines
- Prior diagnosis of COVID-19 documented by a laboratory test. Patients outside of the UCMC medical system will be asked to provide documentation of COVID-19 positive test.
- Complete resolution of symptoms at least 28 days prior to donation
- Female donors who have never been pregnant, previously pregnant female donors negative for HLA antibodies (HLA screening), or male donors

Plasma Donor Subject Exclusion Criteria for Enrollment

- Unable to give consent
- Unable to donate blood per blood bank standard guidelines
- Unsuccessful blood donation

Plasma Recipient Subject Inclusion Criteria for Enrollment

- Patients must be 18 years of age or older
- Must have laboratory-confirmed COVID-19
- Must have severe or immediately life-threatening COVID-19
 - Severe defined as dyspnea, respiratory frequency \geq 30/min, blood oxygen saturation \leq 93%, partial pressure of arterial oxygen to fraction of inspired oxygen ratio $<$ 300, and/or lung infiltrates $>$ 50% within 24 to 48 hours

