A secure email address at the University of Chicago has been made. . Emails to this address will generate an automatic reply (detailed in the attached recruitment materials). Emails will be viewed by the study staff who will be able to respond if potential participants want to learn more about this research study.

Schedule of Events

Schedule of Events for Plasma Donor Subjects

Table 1. Schedule of events for plasma donor subjects:

| Study period | Screen | Enroll | | Donation |
|--|-----------------|-----------------|--|----------|
| Day | -90 to -28 days | -1 days or more | | 0 |
| Test positive for COVID-19 Patients outside of the UCMC medical system will be asked to provide documentation of COVID-19 positive test | x | | | |
| Subject recruitment and screening | | x | | |
| Consent for participation in donor portion of study | | X | | |
| Donor intake questionnaire via redcap. | | X | | |
| Consent for blood donation using standard UCM Blood Donation processes and procedure | | | | x |
| Donation at UCMC Blood Bank | | | | x |

Table 2: Schedule of Events for Plasma Recipient Subject

| Study period | Screen | Baseline | Transfusion | Follow-up | | | | |
|---|---------|----------|-------------------|-----------|---|---|----|-----------------|
| Day | -7 to 0 | 0 | 0 | 1 | 3 | 7 | 14 | 28 ¹ |
| Eligibility | | | | | | | | |
| Informed consent | x | | | | | | | |
| Demographic and Medical history | x | | | | | | | |
| COVID-19 symptom screen | x | | | | | | | |
| Pregnancy test | x | | | | | | | |
| ABO | x | | | | | | | |
| Application for single patient eIND | x | | | | | | | |
| FDA compassionate use for convalescent plasma | | | | | | | | |
| eIND is approved | x | | | | | | | |
| Study Plasma Administration | | | | | | | | |
| Plasma infusion | | | x | | | | | |
| Study Procedures | | | | | | | | |
| Vital signs | x | x | xxxx ² | x | x | x | x | |
| Physical examination | x | | x | x | | x | | |
| Symptom screen | x | x | x | x | x | x | x | x |
| Concomitant medications | x | x | x | | | | | |
| Assessment with 7-point ordinal scale | | x | | x | x | x | x | x |
| Adverse event monitoring | | x | x | x | x | x | x | x |
| Laboratory testing | | | | | | | | |
| CBC and CMP | | x | | x | x | x | x | |
| Chest x-ray or CT chest if available | x | | | x | x | x | x | |
| SARS-CoV-2 RT-PCR | | x | | x | x | x | x | |
| Blood samples for biomarker tests performed in the research lab | | x | | x | x | x | x | |

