- If an AE develops during infusion, the infusion may be slowed or stopped as per investigator's decision.
 - Most reactions to plasma are relatively minor and the infusion can generally be continued. Infusion site burning and non-allergic systemic effects can generally be managed with slowing of the infusion. Infusion can generally be continued in cases of itching or hives after pausing the transfusion, administering antihistamines, and observing the patient for worsening.
 - Severe allergic reactions such as, bronchospasm and hypotension, and may require discontinuation of the infusion.

Concomitant medications will be documented on the CRF

- Prescription medications
- Over the counter medications

- Herbal treatments/nutritional supplements
- Blood products

Statistical considerations

Statistical Analysis

This is a pilot study focused on determining the protocol feasibility with limited subject enrollment. Therefore, statistical analysis will include descriptive summaries of both the primary and secondary outcomes of interest. For continuous variables we will determine: median, minimum and maximum values. Categorical variables will be summarized by the frequency. Unless otherwise indicated, percentages in tables will be column percentages, using the total number of observations in the population ($n=10$), as the denominator. Percentages will be rounded to one decimal place, and thus may not always add up to exactly 100%. Clinical laboratory values will be first reported in using International System of Units (SI).

Analysis of AE data

Analysis of AE data will primarily be descriptive based on MedDRA coding of events. The proportion of subjects experiencing an SAE and the proportion experiencing a Grade 3 or higher AE will be measured.

Analysis of SARS-CoV-2 viremia

Analysis of SARS-CoV-2 viremia will primarily be descriptive, comparing the viremia levels at days 0,1,3,7 and 14 between the subject recipients.

Analysis of research biomarkers

Analysis of biomarker tests performed in the research lab such as antibody titers, cytokine levels will primarily be descriptive, comparing the titers at days 0,1,3,7 and 14 between subject recipients.

Endpoints

Primary Endpoint:

1. Feasibility of performing study pathway consisting of consenting convalescent donors, harvesting convalescent plasma, application for FDA eIND and administering convalescent plasma to the patients

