2. Type and duration of respiratory support (e.g. CPAP, BiPAP, high-flow nasal cannula, mechanical ventilation)

Secondary endpoints:

1. Cardio-circulatory arrest (at any time)
2. Transfer to ICU
3. ICU mortality and LOS
4. Hospital mortality and LOS
5. Ventilator-free days
6. 60 day mortality

Primary Safety Endpoints:

1. Rapid deterioration of respiratory or clinical status on transfusion of anti-SARS-CoV-2 convalescent plasma
2. Cumulative incidence of serious adverse events during the study period: transfusion reaction (fever, rash), transfusion related acute lung injury (TRALI), transfusion associated circulatory overload (TACO), transfusion related infection

Secondary Endpoints

1. Rates and duration of SARS-CoV-2 PCR positivity (RT-PCR) at days 0, 3, 7, and 14.

Study procedures for plasma donors

Study procedures for plasma donors who enter the study through the following mechanisms:

- Patients who are on the list of COVID-19 positive patients maintained by the infectious disease team at the University of Chicago Medical Center (UCMC)
- The primary care physician or a treatment team attending of patients who are on the list of COVID-19 positive patients maintained by the infectious disease team at the University of Chicago Medical Center.
- People who are undergoing COVID-19 testing at UCMC.
- Advertisement of this study will take place in community bulletins, throughout the university with posters/fliers, on the internet, UCMC press release and in the local news to ask whether anyone would like to donate blood and participate in this research study.

Day -28 to -90:

- Tested positive for COVID-19. People outside of the UCMC medical system will be asked to provide documentation of COVID-19 positive test.

Day -28 to -90:

- Complete resolution of all COVID-19 symptoms

Day -1 or more:

- Screening for plasma donor inclusion criteria
- Consent for participation in donor portion of study
- Donor questionnaire

Day 0:

- Consent for blood donation using standard UCM Blood Donation processes and procedure
- Blood donation at the UCM Blood Donation Center

Study procedures for investigational plasma recipient

Day -7 to 0:

1. Screening for patient inclusion criteria
2. Subject informed consent (obtained before performing study related activities).

3. Baseline Evaluation (at screening) (much of the information will be obtained from the medical record)
 - Demographics (Age, sex ethnicity, race)

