 - Medical history (timing of exposure to COVID-19 source patient, acute and chronic medical condition, medications, allergies, any drug trial therapy. Any medical condition arising after consent should be recorded as AE)
 - COVID-19 symptom screen (fevers, cough, shortness of breath), day of onset of symptoms
 - Vital signs
 - COVID-19 testing (RT-PCR) from nasopharyngeal, throat, blood or stool (optional) samples. Other clinically-approved SARS-CoV-2 testing may be used if available (e.g. saliva, nares, blood).
 - Blood typing, CBC, comprehensive metabolic panel
 - Urine or serum pregnancy test for females of childbearing potential. Results from laboratory tests obtained up to 7 days before enrollment may be used for the pregnancy test.
 - Stored samples for biomarker tests performed in the research lab (e.g. antibody titer, cytokines)
 - Determination of eligibility as per inclusion/exclusion criteria
4. Application and approval of eIND per FDA guidelines for single patient compassionate use of convalescent plasma

DAY 0:

1. Study Plasma Administration: 1 unit of plasma will be transfused. Time at start and end of infusion will be recorded and Vital signs will be measured immediately prior to infusion, 10-20 minutes after start of infusion, at completion of infusion and 30-60 minutes after the end of the infusion
2. COVID-19 symptom screen (fevers, cough, shortness of breath)
3. Assessment of clinical status (7-point ordinal scale)
4. New medical conditions, concomitant medication, AE evaluation
5. physical examination
6. Blood typing, CBC, comprehensive metabolic panel, C-reactive protein
7. Stored samples for biomarker tests performed in the research lab (e.g. antibody titer, cytokines)

Day 1-7 (or for duration of hospitalization)

1. Vital signs daily
2. COVID-19 symptom screen (fevers, cough, shortness of breath)
3. Assessment of clinical status (7-point ordinal scale)
4. New medical conditions, AE evaluation
5. physical examination
6. CBC, comprehensive metabolic panel, CRP daily
7. COVID-19 testing (RT-PCR) from nasopharyngeal, throat, blood or stool (optional) samples. Other clinically-approved SARS-CoV-2 testing may be used if available (e.g. saliva, nares, blood)

8. Stored samples for biomarker tests performed in the research lab (e.g. antibody titer, cytokines)

Day 28:

Key issues to consider follow up by phone, alive, at home, in hospital (ICU or not), on supplemental O2 or not, back to work, fully, partially, SNF, nursing home, LTAC

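### Table percentages default to a printed n=10 with no stated exception; read literally, visit-based percentages such as PCR positivity shrink when results are missing

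*Combined protocol and SAP*

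**What the plan says.** All references are to the combined protocol and SAP.

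- **Denominator.** Statistical Analysis sets column percentages "using the total number of observations in the population ($n=10$), as the denominator", as a default that gives way to any exception stated elsewhere. None is stated. The paragraphs on adverse events, viremia and biomarkers name no denominator, and no section gives a rule for missing results.
- **Rounding.** The next sentence reads "Percentages will be rounded to one decimal place, and thus may not always add up to exactly 100" percent. Rounding is the only reason given for totals that miss 100%.
- **Safety.** Analysis of AE data says "The proportion of subjects experiencing an SAE and the proportion experiencing a Grade 3 or higher AE will be measured".
- **PCR.** A secondary endpoint is "Rates and duration of SARS-CoV-2 PCR positivity (RT-PCR) at days 0, 3, 7, and 14". Table 2 schedules the test at baseline and on Days 1, 3, 7 and 14: "SARS-CoV-2 RT-PCR | | x | | x | x | x | x". The recipient procedures list follow-up PCR only under the heading "Day 1-7 (or for duration of hospitalization"; the next heading is Day 28, with follow-up by phone.
- **Number of recipients.** Study Design says "A total of 10 eligible recipient subjects will receive anti-SARS-CoV-2 plasma". Item 1a of the Primary Objective defines feasibility as 6 to 7 of 10 completing the infusion with at least 24 hours of data. Subject Withdrawal says that withdrawals are not replaced. Definitions has "Screen Failures: signed informed consent, but then determined to be ineligible or withdraws".

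**The concern.** A fixed denominator suits a quantity defined for every planned recipient, such as the feasibility count. It does not suit a result that exists only for those sampled at a visit. Recipients are hospitalized with severe or life-threatening disease, withdrawals are not replaced, and the procedure text ties follow-up PCR to the first week or the hospital stay. Fewer than 10 results at a later visit is therefore foreseeable.

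Over a fixed 10, a recipient with no swab counts as not positive in the positive row and as not negative in the negative row. Reported positivity can then fall from visit to visit only because fewer people are swabbed. In a single-group study of an antiviral product, a reader would naturally take that fall as clearance, and there is no control group to expose it.

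**Working it through.** **1. The plan's own figure.** The printed 10 agrees with the 10 recipients in Sample Size, in Study Design and in item 1a of the Primary Objective. It is the planned recipient number.

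**2. The rounding sentence.** Over 10 the only possible percentages are 0.0, 10.0, ..., 100.0, so nothing is ever rounded. Among denominators 1 to 10, only 3, 6, 7 and 9 produce percentages that need rounding at one decimal. The sentence therefore has effect only with some denominator other than 10.

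**3. Size of the scaling.** Let m recipients have a result at a visit and x of them be positive. The literal rule prints x/10 = (x/m) × (m/10). The factor m/10 is also the highest positivity that can be printed, reached when every tested recipient is positive. The documents give no missing rate, so the range of m is assumed.

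| m | factor m/10 | highest printable positivity |
|---|---|---|
| 10 | 1.0 | 100.0% |
| 9 | 0.9 | 90.0% |
| 8 | 0.8 | 80.0% |
| 7 | 0.7 | 70.0% |
| 6 | 0.6 | 60.0% |
| 5 | 0.5 | 50.0% |

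The two figures agree when m = 10 or x = 0.

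**4. Illustration for PCR.** All counts are assumed: 10 infused, half of those swabbed positive each time. The bounds for all 10 are x/10 (every missing swab negative) to (x + 10 − m)/10 (every missing swab positive). They treat every absent result as a missing swab in a living recipient; for someone who has died, positivity at a later visit is not defined.

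| Visit | x of m | printed x/10 | among tested x/m | bounds for all 10 |
|---|---|---|---|---|
| Day 3 | 4 of 8 | 40.0% | 50.0% | 40.0% to 60.0% |
| Day 7 | 3 of 6 | 30.0% | 50.0% | 30.0% to 70.0% |
| Day 14 | 2 of 4 | 20.0% | 50.0% | 20.0% to 80.0% |

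The printed figure falls by 40.0 − 20.0 = 20 points while positivity among those tested does not move. Each printed figure is the lower bound. If missing subjects have no row, the Day 14 positive and negative rows add to 20.0% + 20.0% = 40.0%, which rounding cannot explain.

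**5. Safety proportions.** The same algebra applies with m as the number who started an infusion, if 10 is kept and every counted event is in an infused recipient. With an assumed 2 recipients having an SAE, the literal rule always prints 2/10 = 20.0%. The proportion of those infused is 20.0% at m = 10, 22.2% at 9, 25.0% at 8, 28.6% at 7 and 33.3% at 6.

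**The case against.** Several points on the other side have force.

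- **The wording allows another reading.** The total number of observations may mean the number observed, with 10 in brackets only as the planned size. The rounding sentence favours this. This stands: dilution follows from one of two readings. It does not excuse the text, because the same data would then support two different percentages.
- **A missing row would cure the display.** If subjects without a result have their own row, x/10 is transparent and columns total 100%. This stands too. The plan neither asks for such a row nor rules it out.
- **No PCR percentage table is specified.** The viremia paragraph speaks of levels, and categorical variables are also summarized by frequency. This stands in part: the objectives and endpoints do call for rates of positivity.
- **The sizes are invented.** Table 2 schedules Day 14 PCR for every recipient, and the lack of a Day 14 heading in the procedures does not show that swabs will be missing. A reader might infer that most Day 14 results will be absent. The documents give no missing rate and do not support that.
- **Percentages among the tested are selected.** This is true: the Day 14 bounds show that neither 20.0% nor 50.0% is established for all 10.

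A reader might also infer that the safety proportions are understated as a matter of course. The documents do not support this. Study Design plans that all 10 receive plasma, and a consented subject who withdraws or proves ineligible before infusion may already be a screen failure, outside the 10. The sections also disagree on whether adverse events count from consent (Baseline Evaluation) or from first administration (Reporting Interval). That is a separate point and should be handled as one.

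**Conclusion.** The concern holds as a minor flaw. The default denominator has no stated exception and does not fit the rounding sentence beside it. Taken literally, it scales every non-zero visit-based percentage by m/10 whenever m is below 10. The algebra is exact; the examples rest wholly on assumed counts, and a misleading display also requires that missing subjects not be shown. The safety effect arises only if fewer than 10 recipients start an infusion, at least one event occurs and 10 is still used.

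No decision turns on these percentages. The analysis is descriptive, and the feasibility criterion and numeric halting rules are in counts. What is at risk is a reader's impression of the virologic course.

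**What to change.** Delete the fixed 10 from the denominator sentence and state three denominators:

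1. **Feasibility criterion only:** the 10 proposed recipients.
2. **Adverse events, SAEs, Grade 3 or higher events and whole-cohort clinical outcomes** (such as mortality and cardio-circulatory arrest): the actual number who started an infusion, completed or not, shown as n/N.
3. **Every visit-based categorical variable** (PCR, laboratory categories, 7-point scale, symptom screen, respiratory support): the number assessed at that visit, shown as x/m, with the numbers died, discharged and missing alongside. A footnote should say that those assessed are a selected group. If the 7-point scale has a category for death, deaths belong in that category and in m.

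The rounding sentence can then stay as it is. The cost is a short wording change and table footnotes. No new data are needed, since the infusion start time is already recorded on Day 0. The sponsor should expect safety percentages to look less favourable if fewer than 10 are infused (in the example, 33.3% against 20.0% with 6 infused) and to be unchanged if all 10 are.
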